Stage 1 informed consent. Prior to the baseline assessment, participants will review an online consent with a study staff member of zoom detailing the procedures for the first three months of the pilot SMART and indicate whether they consent to participate.

We have elected implement sequential informed consents for this project for two primary reasons. First, the study procedures are complex and dependent on whether participants respond to the first-stage intervention. Sequential informed consent procedures enhance the comprehension of this complex SMART protocol. Second, because one of the interventions involves receiving CM incentives this could create a scenario where participants initially randomized to MI choose not to respond in order to have another chance to receive CM incentives in the second-stage intervention. Conducting sequential informed consenting substantially mitigates this concern because participants are not aware of the second-stage interventions until the 3-month follow-up assessment. Given these ethical and logistical concerns, we believe sequential informed consenting is a reasonable solution.

Baseline assessment. Due to the challenges presented by COVID-19, we are requesting a waiver of written consent to review the Stage 1 consent with

IRB Study Number: 20180823

Version #10.1; April 2023

participants over zoom at baseline. We will follow-up with remote HIV testing. Participants will be asked to indicate whether they consent to participate in the study and continue with the baseline assessment via Zoom. The baseline quantitative and qualitative assessment includes a detailed battery of measures and a brief in-depth qualitative interview. A codebook of the baseline quantitative measures as well as the qualitative interview guide are attached. Participants will receive a \$50 Amazon gift card or cash application payment for completing this assessment.

Remote HIV testing. To ensure that participants meet the inclusion criteria for Phase II, they will be asked to complete remote HIV testing by mailing in a saliva sample from a kit that our team will send to their home. Participants will receive \$25 as an Amazon gift card or cash application payment for completing remote HIV testing. Those who test positive for HIV will be excluded from this trial and referred for confirmatory testing in their local community.

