Breach of Confidentiality. To mitigate confidentiality risks, all study files are located in a locked file cabinet in a secure filing cabinet. Web-based data collection is employed such that all data is collected and stored behind the University of Miami firewall. All participants are also informed of mandated reporting guidelines for active suicidal/homicidal ideation, child abuse, and elder/dependent adult abuse in Florida. Because this study is funded by NIH, our notice of grant award includes a Federal certificate of confidentiality for this project to protect against court-ordered disclosure of study-related information given the highly sensitive nature of

IRB Study Number: 20180823

Version #10.1; April 2023

the data collected. All assessment interview and intervention activities will be conducted via zoom, which is HIPAA compliant.

Negative Psychological Reactions to Study Procedures. In our experience, the vast majority of participants experience only transient negative reactions to completing HIV testing, self-report assessments, or clinical interviews. On rare instances, participants have experienced more severe negative reactions to study procedures. [name] is a licensed psychologist in Florida. Data collection for this project will be exclusively conducted at the University of Miami. [name] will assist with data collection in Miami and will have access to study data.

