Staff will receive extensive training and supervision to assess participants for signs of acute distress during the study visits. Staff will be trained in a brief screening protocol to assess suicidal thoughts, plans and intent. Specifically, they will administer a brief screening tool only where participants display signs of acute distress. Those expressing any current plan or intent to harm themselves or someone else will be assessed further by the study PI, a licensed psychologist in Florida. The vast majority of participants displaying signs of acute distress (e.g., crying) will not report any current plan or intent. Referral sheets are available to provide linkages with community-based resources such as mental health treatment and substance abuse treatment that may assist participants with managing some of the issues that come up in their study activities. Those who test positive for HIV will be immediately linked to confirmatory testing and immediate anti-retroviral therapy (ART) with [name]. We will also work with [name] to refer any participants who are newly diagnosed with HIV to the appropriate case management services at the Miami-Dade County Department of Health to assist these individuals with access HIV medical care.

We acknowledge that participants who learn they test positive for HIV may experience acute distress. [name] is a licensed psychologist and we are prepared to provide immediate, on-site support to assist participants in coping with acute distress, ensure there is no imminent threat of harm to self or others, and coordinate immediate linkage for confirmatory HIV testing. We will also provide referrals for community-based mental health treatment tailored specifically to meet the needs of those who are newly diagnosed.

7) **Data and Specimen Banking***

There will be no specimen banking in this modified protocol. Saliva samples provided by participants will be labeled only with the participant ID and date of receipt. These saliva samples will be tested for HIV by a collaborating laboratory and then destroyed.

IRB Study Number: 20180823
Version #10.1; April 2023

8) Data Management*

All patient-reported data will be stored on a secure server and labeled with the participant ID number only. Participant files will be completed using Redcap. Any paper files will be stored in a locked filing cabinet in [name] office.

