All study procedures will occur at the University of Miami Miller School of Medicine. We will use a national sampling frame to recruit participants from social networking applications (e.g., Scruff, Grindr). We also plan to recruit participants from South Florida in partnership with local STI and PrEP clinics serving MSM in South Florida that are operated by the Miami Department of Health and AIDS Healthcare Foundation. [name] is an external collaborator on this project but no data will be collected at his site in New York. He will assist with data collection in Miami as needed and have access to study data.

13) **Resources Available**

[name] has extensive expertise in the designing and conducting clinical research with stimulant-using MSM. He has overseen multiple protocols that collected biospecimens for specimen banking with substance-using populations.

14) **Prior Approvals**

This study was previously submitted to the IRB for approval as part of a just-in-time (JIT) request. We are modifying this protocol to recruit a national sample and to be conducted entirely online due to difficulties with achieving our enrollment targets in South Florida.

15) **Recruitment Methods**

The primary mechanism for recruiting participants will be using social networking applications (e.g., Scruff, Grindr). Participants residing in the United States and Puerto Rico will be directed to a secure Redcap survey where the phone screening questions are administered. Participants will be asked to provide their contact information (i.e., name, phone number, and email) if they wish to be contacted by the study team to learn more information.

IRB Study Number: 20180823

Version #10.1; April 2023

Community-based recruitment will occur broadly in the community using palm cards and pull-tab flyers that will be distributed at bars and clubs, social media (e.g., Facebook), social networking applications (e.g., Grindr, Scruff), medical clinics that prescribe PrEP, referrals from active participants, and face-to-face recruitment at community events (e.g., Pride). Potentially eligible participants who contact the study team will complete a brief telephone screen or Redcap survey to determine eligibility. Flyers have been approved by the IRB, including recruitment banner ads that will be used on social networking applications (e.g., Scruff, Grindr).

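### The Risks section sends every newly diagnosed participant to Miami-Dade case management, and all who test positive to one named ART provider, although recruitment is now national and the study is online

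*Protocol*

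**What the plan says.** Protocol section 6 (Risks), under Negative Psychological Reactions to Study Procedures, makes three commitments for participants found to have HIV:

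- **ART linkage:** "Those who test positive for HIV will be immediately linked to confirmatory testing and immediate anti-retroviral therapy (ART", followed by the name of one provider, which is removed from the public text.
- **Case management:** the team will "refer any participants who are newly diagnosed with HIV to the appropriate case management services at the Miami-Dade County Department of Health". The stated purpose is to help these people get HIV medical care.
- **Distress support:** "we are prepared to provide immediate, on-site support to assist participants in coping with acute distress".

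None of the three carries a residence condition. The same part of section 6 adds a referral that is not tied to any place: "We will also provide referrals for community-based mental health treatment tailored specifically to meet the needs of those who are newly diagnosed".

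The design around this text is national and remote. Section 14 (Prior Approvals) says "We are modifying this protocol to recruit a national sample and to be conducted entirely online". Section 15 (Recruitment Methods) says "Participants residing in the United States and Puerto Rico will be directed to a secure Redcap survey". Section 6, under Breach of Confidentiality, says "All assessment interview and intervention activities will be conducted via zoom, which is HIPAA compliant". Section 5, under Remote HIV testing, has participants "mailing in a saliva sample from a kit that our team will send to their home".

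Section 5 also says what follows a positive result. The person leaves the trial and is referred for confirmatory testing where he lives. A separate sentence describes referral of Miami-Dade residents to a named provider for confirmatory testing and ART. The SAP does not address care after a positive test.

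**The concern.** The protocol was changed from a South Florida study to a national online one. Section 5 took account of the change, but section 6 did not receive the matching edit. The word *any* in the case-management sentence makes the rule universal, and the destination is a single county health department.

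The main recruitment channel is social networking applications used across the country, so a newly diagnosed participant who lives outside Miami-Dade is a foreseeable case. Staff who follow the sentence as written would refer him to a county service where he does not live, soon after a serious diagnosis. What is at stake is his access to care. The trial's results are not at stake.

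**Working it through.** The point has no stated figure to reproduce and no arithmetic applies, so the check is a comparison of the two sections step by step.

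| Step after a positive result | Section 5 | Section 6 | Route stated for a non-resident of Miami-Dade |
|---|---|---|---|
| Confirmatory testing | Local community; named provider described for Miami-Dade residents | Immediate linkage for all | Yes, local |
| ART | Named provider, described for Miami-Dade residents | One named provider, for all | Unclear |
| HIV case management | Not mentioned | Miami-Dade County, for any newly diagnosed participant | None outside Miami-Dade |
| Support in acute distress | Staff training and supervision in counseling | On-site support, a brief suicide screen, further assessment by the study PI, referral sheets | Yes, but the word on-site does not fit |
| Mental health referral | Not mentioned | Community-based, no place named | Yes |

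Reading across the rows:

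1. **Confirmatory testing.** Section 5 gives a usable local route, so nothing is missing at this step.
2. **ART.** Section 6 covers everyone but through one provider. Section 5 describes its provider for Miami-Dade residents but does not say that only residents may use it. How the two sentences fit together for a non-resident is unclear. Both provider names are removed from the public text, so the reader cannot confirm that they are the same person or where the section 6 provider practices.
3. **Case management.** This is the clear defect. It comes after diagnosis, so local confirmatory testing does not supply it. The only route in either document is Miami-Dade. The qualifier about appropriate services chooses among services at that department and does not point to another jurisdiction.
4. **Distress support.** The tasks listed in section 6 are coping support, checking for imminent harm and coordinating linkage. All can be done by Zoom or telephone. Only the adjective is out of date.

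**How many people.** The expected number affected is N × r × s, where N is the number tested, r the proportion newly diagnosed and s the share of those living outside Miami-Dade. The planned Phase II sample is 70, but N may exceed it because testing precedes randomization. The documents give neither r nor s, so no count is offered.

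**Effect on the analysis.** Section 5 excludes people who test positive and confines the randomization visit to those confirmed HIV-negative. They therefore do not enter the randomized comparison, and changing their referral route alters no estimate.

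**The case against.** The best defense is that section 5 is the operative text and section 6 is risk narrative. Read together, the Miami wording in section 6 is naturally the branch for Miami participants. South Florida recruitment continues, so that wording remains right for some people. A non-resident is first referred to local confirmatory testing and is not sent to Miami at the outset. Staff are trained in linkage and in counseling people in distress. Referral sheets exist, and the examples given of what they cover are not exhaustive. They may list local HIV services.

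Much of this stands. It disposes of three stronger readings that a reader might infer:

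- **That non-residents have no plan after a positive test.** Section 5 gives local confirmatory testing, and section 6 gives mental health referral without a place limit.
- **That distress support is absent for remote participants.** The listed tasks can be done remotely, and other safeguards (staff counseling, suicide screening, assessment by the PI) are not tied to a site by their wording.
- **That participants were in fact misreferred.** The referral sheets and staff linkage procedures are not in the available text, so nothing can be said about their contents or about practice.

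The defense does not reach the case-management sentence. Section 5 never mentions case management, so it cannot limit or replace the section 6 rule. Even if the referral sheets list local services, the protocol still directs every newly diagnosed participant to one county.

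**Conclusion.** The point holds as a participant-safety correction to section 6. The case-management rule, followed as written, misdirects anyone living outside Miami-Dade. The ART linkage is universal in section 6 and described for Miami-Dade residents in section 5, and the two need to be reconciled. The on-site wording is a minor correction.

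The frequency is likely low and cannot be derived. There is no effect on sample size, error rates or analysis. The conclusion assumes that the visible protocol text is what staff are meant to follow. It would weaken if the linkage procedures or referral sheets already give local HIV case management, although the protocol sentence would still need correcting.

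The SAP is written in the past tense, which suggests that the pilot has been carried out. The remaining value of the correction is then mainly for the full-scale SMART that this pilot is meant to inform, where the same text could be reused.

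**What to change.** In section 6, under Negative Psychological Reactions to Study Procedures:

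1. Limit the Miami-Dade case-management referral and the named-provider ART linkage to participants who live in Miami-Dade County, in line with section 5.
2. State that all other participants are referred to ART and HIV case management in their own jurisdiction, after the local confirmatory testing that section 5 already provides.
3. As a minor wording correction, replace on-site support with support by Zoom or telephone.

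This takes two or three sentences. The cost is one IRB modification and some staff time to identify ART and case-management services where participants live. Data collection, sample size and analysis are unchanged.

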In-depth qualitative interviews with stimulant-using MSM. In-depth interviews with stimulant-using MSM will be approximately one hour and cover topics such as history of stimulant use, attitudes and beliefs about PrEP. Those who are not on PrEP will be asked to describe on barriers and facilitators to accessing PrEP. Those who are currently taking PrEP will be asked to describe how they successfully

IRB Study Number: 20180823

Version #10.1; April 2023

navigated the process of initiation and strategies they are implementing to achieve prevention effective PrEP adherence. After completing the interview, participants will complete a brief survey to assess demographic information and efforts to navigate the PrEP healthcare continuum (see attached). Stimulant-using MSM will receive \$40 for completing this one time study visit.

[figure not shown]
Phase II – We will conduct a pilot SMART with 70 HIV-negative, stimulant-using MSM who meet CDC criteria for PrEP eligibility.

First Stage Intervention. After completing a baseline assessment and a brief run-in period, participants will be randomized to complete a 3-month CM intervention or a two-session MI intervention that were developed as part of our Phase I activities.

Second Stage Intervention. Three months after this first-stage randomization, participants will complete a second informed consent prior to a 3-month follow-up assessment to determine whether they are responders.

[figure not shown]
Experimental Conditions. Responders will be classified as those who have started PrEP, the primary outcome. Responders will continue with assessments only.

Participants who have not responded to the initial intervention will be randomized again to either: 1) continue with assessments only; or 2) switch to the other intervention (i.e., CM+MI versus MI+CM). An overview of the pilot SMART procedures is provided in the figure below. Below we describe each of the procedures relevant to executing this pilot SMART.

Telephone screen. Stimulant-using MSM will complete a brief telephone screen to determine eligibility for enrolling in the pilot SMART based on inclusion criteria above for Phase II (see attached). This telephone screen has been modified to include items relevant to the novel coronavirus (COVID-19), which are also attached. The figure below describes the participant flow for the pilot SMART.

PRISM 2.0 Study Flow Diagram

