Non-reactive (HIV-) test results will be delivered to participants as part of their randomization visit. For those who do not respond to attempts to schedule their randomization visit, after 2 months their non-reactive HIV test results will be emailed to the email address on file via a secure, encrypted University of Miami email. This report does not contain any PHI.

All study staff also receive ongoing training and supervision from [name] (a licensed psychologist) on delivering HIV test results and providing counseling to individuals experiencing acute distress. All staff will receive training in procedures for immediate linkage to confirmatory HIV testing. Participants residing in Miami-Dade county who are test positive for HIV will be referred for confirmatory testing and anti-retroviral therapy (ART) with [name].

Randomization visit. Approximately one week after baseline, participants who are confirmed to be HIV-negative will attend a separate randomization visit. Those randomized to CM will be introduced to incentives for PrEP clinical evaluation and uptake. Participants randomized to MI will receive their first session of this intervention. All participants will receive a \$20 Amazon gift card or secure cash application payment for attending the randomization visit.

CM intervention protocol. Participant randomized to CM will complete a 3-month CM protocol where they will be eligible for CM incentives for documentation that they have been evaluated for PrEP by a medical provider (\$50) and filled a prescription for PrEP (\$50) in the three months following randomization. Total possible CM incentives are \$100 per participant, which will be provided in Amazon gift cards or secure cash application payment.

MI protocol. Participants in the MI intervention will complete two individually delivered sessions via zoom designed to enhance intrinsic motivation and self-efficacy for taking the first steps towards starting PrEP and addressing the

IRB Study Number: 20180823

Version #10.1; April 2023

intersection of substance use and HIV risk. Session 1 focuses on supporting efforts of participants to be medically evaluated for PrEP. Session 2 focuses on addressing the intersection of substance use and HIV risk. A detailed protocol for this 2-session MI intervention is attached. Participants will receive a \$20 Amazon gift card or secure cash application payment for completing each MI session via zoom.

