Stage 2 informed consent. Prior to completing the 3-month follow-up assessment, participants will provide informed consent for the Stage 2 of the pilot SMART. This consent will clarify that participants may be invited to participate in a CM or MI intervention based on the responses to the survey questions and prior intervention assignment. Due to the challenges presented by COVID-19, we are requesting a waiver of written consent to review the consent with participants over zoom.

3-month follow-up assessment with second-stage randomization. After completing the informed consent process, we will re-administer quantitative measures from the baseline assessment via Zoom, and those who have not started PrEP will be classified as non-responders. All non-responders will complete the second-stage randomization to either: 1) continue with assessments only; or 2) switch to the other intervention (CM+MI versus MI+CM). Those randomized to receive CM or MI will receive these intervention consistent with the protocols described above. Responders will continue with assessments only. Participants will receive a \$50 Amazon gift card or secure cash application payment for completing this assessment. Participants will have a 30-day window (+1 month) to complete their follow-up assessments.

6-month follow-up assessment. We will re-administer the quantitative measures from the baseline assessment and a qualitative exit interview (see attached) via zoom. Participants will receive a \$50 Amazon gift card or secure cash application payment for completing this assessment. Participants will have a 30-day window (+1 month) to complete their follow-up assessments.

6) Risks

These study procedures meet the criteria for minimal risk research activities. However, possible risks include: 1) a breach of confidentiality; and 2) negative psychological reactions to study procedures.

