Because this is a pilot study, we have not conducted a formal power analysis. In fact, there is increasing recognition in clinical research methods that pilots should focus primarily upon issues relevant to feasibility and acceptability of a more definitive study, not effect size estimation.

Feasibility. To evaluate feasibility of a more definitive trial, we will monitor rates of recruitment and effort required (e.g. number of staff hours) as well as the number of screenings conducted, proportion eligible, and proportion who agree to enroll. *Feasibility of recruitment* will be operationalized as an enrollment rate of 70% or higher, an established standard in the literature. We will also record number of rescheduled and missed assessment visits, CM visits, and MI sessions to estimate staffing needs and retention protocols for a planned R01. *Feasibility of intervention delivery* will be operationalized as attending three-fourths of scheduled MI sessions (3 of 4 sessions completed on average). Although power will be limited, we will conduct independent samples t-tests to describe the average number of MI sessions attended among non-responders randomized to switch (i.e., CM+MI vs. MI+CM).

Acceptability. To measure *acceptability*, we will modify previous intervention satisfaction evaluation surveys that have been administered to methamphetamine users in [name] clinical research. Measures include items such as, "How satisfied were you with the program in general?" and "How likely are you to recommend this intervention to a friend who uses stimulants?" Independent samples t-tests will describe mean acceptability ratings of CM and MI among non-responders who are randomized to switch (i.e., CM+MI vs. MI+CM).

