PrEP Readiness Interventions for Supporting Motivation

[name], ABAP (Contact MPI) & [name], MPH (MPI)

NCT04205487

August 7, 2024

Feasibility. In this pilot SMART, we examined several indices of feasibility. We report randomization rates, completion of MI and CM sessions, fidelity ratings of MI sessions, and follow-up rates over six months.

Acceptability. After the 6-month assessment, participants were given the opportunity to sit for a one-on-one, semi-structured qualitative exit interview via Zoom. The staff member conducting exit interviews was not involved in the primary study procedures to avoid bias. Participants were given an overview of the activities they completed during PRISM (e.g., two MI sessions, CM incentives, and three surveys) and asked about their experiences. Interview guides were tailored to each participant's study arm (MI, CM, or MI+CM) and whether they had filled a PrEP prescription during the intervention (i.e., responders versus non-responders). Exit interviews were approximately 30 minutes and participants received a \$50 incentive.

Qualitative interviews were analyzed using a rapid qualitative analytic approach as a guide (Hamilton, 2020; Harkness et al., 2022). Interviews were first transcribed verbatim and reviewed for quality assurance. Transcriptions were then used to develop a matrix summary of participant responses, including participant number, intervention arm, PrEP status, and responses to each domain of interest. The research team, consisting of a graduate student research assistant, a doctoral level interviewer and a doctoral level project manager, reviewed and discussed the matrix to identify emerging themes, data consistency and matrix accuracy. Illustrative quotes were then extracted to highlight relevant themes. Finally, the manuscript authors reviewed the matrix, themes, and illustrative quotes as well as agreed upon the accuracy of the findings.

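### The delivery-feasibility benchmark is glossed as 3 of 4 MI sessions on average, but no participant is scheduled for more than two; 75% corresponds to a mean of 1.5 of 2

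*Protocol*

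**What the plan says.** The Feasibility paragraph of protocol section 8 sets the standard for intervention delivery as "attending three-fourths of scheduled MI sessions (3 of 4 sessions completed on average". It is the paragraph's only numerical standard for delivery; the other threshold there, 70%, concerns enrollment.

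The length of MI is given in several places, always as two sessions:

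- Protocol section 5, First Stage Intervention: randomization is to "a 3-month CM intervention or a two-session MI intervention".
- Protocol section 5, MI protocol: "Participants in the MI intervention will complete two individually delivered sessions via zoom", and again "A detailed protocol for this 2-session MI intervention is attached".
- SAP, Acceptability: the activities reviewed with participants at the exit interview include "two MI sessions, CM incentives, and three surveys".

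On the second stage, protocol section 5 (Experimental Conditions, and the 3-month follow-up paragraph) gives responders no further intervention. Non-responders are re-randomized either to assessments alone or to "switch to the other intervention (i.e., CM+MI versus MI+CM". Second-stage content is the same as first-stage content: "Those randomized to receive CM or MI will receive these intervention consistent with the protocols described above".

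The SAP's Feasibility paragraph lists completion of MI and CM sessions among the results to be reported, without repeating the 75%.

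**The concern.** The gloss in parentheses is worded as a number of sessions completed on average. Read that way it asks for a mean of 3, which is more sessions than anyone in the trial is scheduled to receive. Feasibility is part of Aim 2, and the protocol says a pilot should concentrate mainly on feasibility and acceptability, so a threshold that decides feasibility ought to fit the intervention it judges.

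What is at stake is limited. Someone comparing the reported mean number of MI sessions with the figure in parentheses would conclude that delivery had failed even if every participant attended every session.

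**Working it through.** **Inputs.** MI has 2 sessions at either stage (protocol section 5; SAP, Acceptability). The second stage offers only assessments or the intervention not yet received (protocol section 5). The benchmark is 75% of scheduled sessions, glossed as 3 of 4 (protocol section 8). The SAP's outcomes section groups the six arms as MI-only (D, E), CM-only (A, B) and both interventions (C, F).

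**Step 1: reproduce the plan's figure.** Threshold in sessions = 0.75 × scheduled sessions. A result of 3 needs 3 / 0.75 = 4 scheduled sessions. With two sessions per course, that means MI at both stages (2 + 2 = 4).

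**Step 2: count scheduled MI sessions on each path.**

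| First stage | Status at 3 months | Second stage | Scheduled MI sessions |
|---|---|---|---|
| CM | Responder | Assessments | 0 |
| CM | Non-responder | Assessments | 0 |
| CM | Non-responder | MI | 2 |
| MI | Responder | Assessments | 2 |
| MI | Non-responder | Assessments | 2 |
| MI | Non-responder | CM | 2 |

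The maximum is 2. The path needed in step 1, MI followed by MI, is not in the design. The SAP's grouping agrees: its two CM-only arms have 0 MI sessions per person and its other four have 2. The flow figures are not available in the text, so the text alone does not show which of C and F began with MI, but both have 2 scheduled sessions.

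**Step 3: check the mean.** If nobody can complete more than 2 sessions, no group mean can exceed 2. A mean of 3 is out of reach in any arm or pooling of arms, even with perfect attendance.

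**Step 4: express the 75% on the actual schedule.** 0.75 × 2 = 1.5, so the matching statement is a mean of at least 1.5 of 2.

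**Step 5: group mean or individual rule.** Applied to each person, 75% of two sessions could be met only by attending both, since 1 of 2 is 50%. The protocol's reference to an average points to the group mean, so 1.5 is the corresponding figure.

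**The case against.** The strongest reply is that three-fourths and 3 of 4 are the same fraction. Nothing has been miscalculated, and the parenthesis may do no more than restate the ratio. That stands in part. The operative rule, three-fourths of scheduled MI sessions, can be applied as written, and the fault is an inconsistency with the schedule rather than an error of arithmetic. The reply does not rescue the parenthesis as worded, because that speaks of sessions completed on average and so invites a count that the design cannot produce.

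Three stronger readings are tempting, and the documents do not support them:

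- *The criterion has no denominator.* It has one: scheduled MI sessions, with no limit by stage or arm. Second-stage MI follows the same protocol as first-stage MI, so the plain reading covers both stages. The next sentence confines a t-test to non-responders who switch, but that limit is not attached to the benchmark. An explicit statement of whose sessions count would be good practice; its absence is missing detail and not an error in itself.
- *The SAP has abandoned the standard.* The SAP reports MI completion, and nothing in it withdraws the protocol's 75%. Its Feasibility paragraph also leaves out the 70% enrollment threshold, so the silence is general and is not directed at this criterion.
- *The figure is left over from a four-session version of MI.* Four sessions would explain the 3, but neither document describes such a schedule, so the origin of the figure is conjecture.

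**Conclusion.** The point holds as a minor inconsistency: the session count attached to the delivery threshold is wrong as written. The text implies a mean of 3, the most that can be scheduled is 2, and the mean corresponding to 75% is 1.5.

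A reader might go further and infer that delivery feasibility cannot be assessed. That does not follow, because the 75% level remains valid and can be applied to the sessions recorded. No sample size or error rate depends on it; the protocol states that no formal power analysis was done.

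The conclusion rests on the written descriptions of the design, which agree across both documents, and on taking the average as a group mean. It needs no assumption about allocation, response rates or attendance.

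**What to change.** Issue a dated clarification in the SAP or the report, and carry it into the protocol if that is amended again. Replace the gloss with: *a mean of at least 1.5 of 2 scheduled MI sessions (75%)*. Then:

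- report MI completion against the 75% standard over all MI sessions scheduled at either stage, which in the SAP's labels means arms C, D, E and F;
- show first-stage and second-stage MI separately alongside the overall figure;
- label the clarification as made after data collection, while noting that the 75% level and the reference to an average were already in the protocol.

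The cost is a sentence or two. No new data are needed, since the protocol already commits to this: "We will also record number of rescheduled and missed assessment visits, CM visits, and MI sessions". The drawback is timing. The SAP describes work already done, so the clarification cannot be presented as prespecified.
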